NON-INTERVENTIONAL (NI) STUDY PROTOCOL

Study information

Title	Effectiveness of BNT162b2 formulations using state vaccine registry and insurance claims data		
Protocol number	C4591065		
Protocol version identifier	1.0		
Date	15 November 2023		
Medicinal product	Pfizer BNT162b2 formulations		
Research question and objectives	What is the real-world effectiveness of BNT162b2 formulations?		
	Primary objective:		
	To evaluate vaccine effectiveness (VE) of BNT162b2 formulations in non-pregnant, non-immunocompromised adults (age 18+) against medically attended COVID-19, mortality, and healthcare resource utilization by age and adapted vaccine formulation.		
	Secondary objectives		
	 To assess VE of BNT162b2 formulations in pediatrics (age < 18) against medically attended COVID-19, non-COVID-19 respiratory infections, mortality, and healthcare resource utilization by age and adapted vaccine formulation. 		
	 To estimate short-term (3A) and long-term (3B) healthcare resource utilization and costs associated with COVID-19 by vaccination status, age, and site of care. 		
	Exploratory objectives		
	To measure VE of BNT162b2 formulations in non-pregnant immunocompromised adults (age 18+) against medically attended COVID-19, mortality and healthcare resource utilization by age and adapted vaccine formulation.		
	 To quantify differences in VE of BNT162b2 formulations in non-pregnant, non-immunocompromised adults (age 18+) when co-administered with seasonal influenza vaccines versus when each vaccine is given separately, by age groups. 		
Author	PPD , PhD, MSc		
	PPD		
	Pfizer Inc.		
	Evidence Generation Platform		

BNT162b2 (COVID-19 vaccine formulations)
C4591065 NON-INTERVENTIONAL STUDY PROTOCOL
Version 1.0, 15 November 2023

PPD

This document contains confidential information belonging to Pfizer. Except as otherwise agreed to in writing, by accepting or reviewing this document, you agree to hold this information in confidence and not copy or disclose it to others (except where required by applicable law) or use it for unauthorized purposes. In the event of any actual or suspected breach of this obligation, Pfizer must be promptly notified.

2. LIST OF ABBREVIATIONS

Abbreviation	Definition
aHR	Adjusted hazard ratio
aRR	Adjusted risk ratio
CDC	Centers for Disease Control and Prevention
CI	Confidence interval
CVX	Clinical Vaccines Administered code
EHR	Electronic health records
EUA	Emergency use authorization
FDA	US Food and Drug Administration
ICD-10-CM	International Classification of Diseases, Tenth Revision, Clinical Modification
ICU	Intensive care unit
IPTW	Inverse probability of treatment weighting
KPSC	Kaiser Permanente of Southern California
OR	Odds ratio
RD	Risk differences
RSV	Respiratory syncytial virus
SMD	Standardized mean differences
TND	Test negative design
NPI	National provider identifier
VE	Vaccine effectiveness
US	United States

4. AMENDMENTS AND UPDATES

None.

5. MILESTONES

Milestone	Planned Date
Start of data collection	01 January 2024
End of data collection	31 March 2024
Final study report	31 May 2024

6. RATIONALE AND BACKGROUND

Administrative claims data have traditionally had limited capabilities for studying vaccinated populations. This limitation is a function of the varied settings in which vaccines may be administered to a patient and whether an individual transaction is generated. Non-medical settings (e.g., workplace, schools, public venues, etc.) and mass events (e.g., vaccination clinics, Federal Emergency Management Agency, etc.) typically only require roster billing for reimbursement. A roster claim form only records the date of vaccine administration; provider's name and national provider identifier (NPI); and patient's ID (e.g., Medicare ID, driver's license, etc.), date of birth, name, gender, and address. Importantly, the roster is submitted with a modified CMS-1500 "cover" claim to capture the vaccine information, however, individual CMS-1500 claims that link the patient information to the cover claim are never generated. Since traditional claims databases capture and report the individual CMS-1500 claim form, vaccinations conducted via roster billing were lost. However, although roster billing does not generate individual CMS-1500 claims, the linkage between the roster and vaccine information are reconciled by various state entities to populate vaccine registries.

Until recently, vaccine registries were not available for de-identification and linkage to secondary claims-based databases. However, through a collaboration with HealthVerity, a leading supplier of secondary health data, the State of California and the State of Louisiana have made their vaccine registries available for linkage for research purposes. California and Louisiana deidentify the registries, using HealthVerity's software to convert each patient's protected health information to a unique HealthVerity ID which can then be linked to the full HealthVerity database to gather clinical history and outcomes. This protocol defines the utilization of HealthVerity data, linked to the State of California/Louisiana's vaccine registry, for studies of VE and uptake for populations of interest.

The ability to link the State of California/Louisiana's vaccine registry to a secondary claims-based database provides a unique opportunity to maximize the capabilities of real-world data and efficiently conduct VE studies on a variety of targeted populations and endpoints, including the updated monovalent XBB.1.5 COVID-19 vaccine formulation.

TABLE 1. TIMELINE OF KEY BNT162B2 REGULATORY MILESTONES

Vaccine formulation	Age group	Event
BNT162b2 monovalent XBB.1.5 COVID- 19 vaccine	Age 12 and older	11 September 2023: U.S. Food and Drug Administration (FDA) approval ²
	Age 6 months to 11 years	11 September 2023: FDA emergency use authorization (EUA) ²
	N/A	15 June 2023: (FDA)'s Vaccines and Related Biological Products Advisory Committee recommended that COVID-19 vaccines for 2023-2024 be updated to a monovalent XBB.1.5 vaccine. ³
BNT162b2 bivalent BA.4/5 COVID-19 vaccine	Age 12 and older	31 August 2022: FDA EUA ⁴
vaccine	Age 5 to 11	12 October 2022: FDA EUA ⁵
	Age 6 months to 4 years	08 December 2022: FDA EUA ⁶
BNT162b2 wild- type booster dose(s) COVID-19 vaccine	Age 5 to 11	17 May 2022: FDA authorized first booster dose
	Age 50 and older, and immunocompromised individuals	29 March 2022: FDA authorized second booster dose
	Age 65 and older, and individuals with potentially high risk that were age 18-64	22 September 2021: FDA authorized single booster dose
BNT162b2 wild- type primary series COVID-19 vaccine	Age 6 months to 4 years	17 June 2022: FDA EUA
	Age 5 to 11	29 October 2021: FDA EUA
	Age 16 and older Age 12 to 15	23 August 2021: FDA approval 10 May 2021: FDA EUA
	Age 16 and older	11 December 2020: FDA EUA

This protocol is not designated as a post-approval safety study (PASS) and is not a commitment to any regulatory bodies.

7. RESEARCH QUESTION AND OBJECTIVES

What is the real-world effectiveness of BNT162b2 formulations?

This study is descriptive in nature and as such does not include any pre-specified hypotheses.

Primary objective:

 To evaluate the VE of BNT162b2 formulations in non-pregnant, non-immunocompromised adults against medically attended COVID-19, mortality and healthcare resource utilization by age and adapted vaccine formulation.

Main summary measure: VE = (1 - adjusted hazard ratio [aHR]) * 100, comparing vaccinated to unvaccinated persons

Secondary objectives

 To assess VE of BNT162b2 formulations in pediatrics against medically attended COVID-19, non-COVID-19 respiratory infections, mortality and healthcare resource utilization by age and adapted vaccine formulation.

Main summary measure: VE = (1 - aHR) * 100, comparing vaccinated to unvaccinated persons

To estimate short-term (3A) and long-term (3B) healthcare resource utilization and costs associated with COVID-19 by vaccination status, age, and site of care.

Main summary measure: Inpatient healthcare expenditure comparing vaccinated to unvaccinated persons (3A), and total healthcare expenditure comparing COVID-19 to non-COVID-19 patients (3B).

Exploratory objectives

 To measure VE of BNT162b2 formulations in non-pregnant immunocompromised adults against medically attended COVID-19, mortality and healthcare resource utilization by age and adapted vaccine formulation.

Main summary measure: VE = (1 - aHR) * 100, comparing vaccinated to unvaccinated persons

 To quantify differences in VE of BNT162b2 formulations in non-pregnant, nonimmunocompromised adults when co-administered with seasonal influenza vaccines versus when each vaccine is given separately, by age groups.

> Main summary measure: aRR to evaluate non-inferiority, comparing people with coadministered vaccines to BNT162b2 vaccine alone for COVID-19-related outcomes

> Main summary measure: aRR to evaluate non-inferiority, comparing people with coadministered vaccines to seasonal influenza vaccine alone for influenza-related outcomes

8. RESEARCH METHODS

We will utilize a target trial emulation design in order to identify patients for follow-up based on qualifying events. The target trial emulation design is a pragmatic framework that reflects real-life clinical behaviors of non-randomized exposures and subsequent outcomes (see Table 1).

A test-negative design (TND), which is a modified form of a case-control study, is commonly used in VE studies. In the TND, cases and controls are identified from persons who sought testing for a pathogen, which may increase comparability between groups as there is an association with vaccination and healthcare seeking behavior. However, for this study a retrospective cohort design was chosen over the TND for the following reasons:

- Administrative claims data do not contain test results, which would be a necessary data element for conducting a TND study. While HealthVerity offers the option to potentially add EHR data, and separately tokenization to laboratory results through LabCorp or Quest, this is not part of the current suite of purchased data.
- Given the end of the COVID-19 Public Health Emergency in May 2023, COVID-19 tests are no longer required to be covered by private or public insurers unless ordered by a physician.^{8,9} This may create selection bias, in that persons paying out of pocket to access testing likely differ from those who are not testing. 10 A TND of those who have sought testing for COVID-19 has the potential for estimates that are different from the general population, ¹¹ owing to distorted associations between factors related to healthcare seeking in the analysis population compared with the general population.¹²
 - a. If those testing at their own expense are more likely to become diagnosed with COVID-19, such as those at higher risk of severe disease, then VE estimates would be biased towards the null.
 - Conversely, if there was a healthy-user effect or increased uptake among higher socioeconomic position groups, VE estimates would be biased away from the null.
- A key assumption of the TND is that exposure (here, COVID-19 vaccination) does not impact the probability of selection in the case (a positive test result on a COVID-19 test) or control population (a negative test result on a COVID-19 test). It is possible that vaccinated persons may be less likely to be seek testing in order to become a case than unvaccinated persons. This, if present, would create collider stratification bias via the requirement for testing in a TND, which biases estimates away from the null and may lead to overestimations of VE. 12-14
- Owing to the case-control nature of the design, TND allows for estimation of odds ratios (OR) but not hazard or risk ratios. OR are not directly interpretable as percentage reduction in risk, which is an easily interpretable summary measure of VE. OR with a protective direction of effect (ratio < 1) will underestimate risk, leading to underestimations of VE. 15 A cohort design allows for absolute estimates of risk such as risk differences.

The use of a retrospective cohort study allows for the adoption of design principles of randomized control trials to help mitigate some of these biases.

Cohort identification will begin from the date of EUA or FDA approval for the BNT162b2 formulation. Study follow-up will occur from FDA EUA or approval date until COVID-19 diagnosis or other outcome of interest (hospitalization, emergency department visit, outpatient encounter, end of medical and/or pharmacy enrollment, or death [according to the mortality database]).

In aims 1, 2 and 4, vaccination status will be measured as a time-varying exposure. In aims 3 and 5, vaccination status will be measured as a time-fixed exposure. Exposed person-time begins 14 days after receipt of a BNT162b2 formulation. Unexposed person-time is unvaccinated person-time, as well as 0-13 days after vaccination. The unexposed group will be further stratified by previous vaccination status for relative VE: XBB.1.5 unvaccinated and BA.4/5 vaccinated; XBB.1.5 and BA.4/5 unvaccinated and at least 2 doses of mRNA vaccine (regardless of formulation), never COVID-19 vaccinated.

The full data available, from 01 December 2018, will be used as the look-back period to define patient's characteristics, clinical history, risk factors, and healthcare utilization.

TABLE 2. TARGET TRIAL AND TARGET TRIAL EMULATION

Target Trial Specification ^{16,17}	Target Trial Emulation			
Eligibility criteria				
Inclusion criteria in trials generally reflected age-related eligibility for vaccination.	For brevity, we will not discuss each of the 5 aim's different inclusion criteria here. Throughout, we used age at time vaccine was authorized or approved by FDA for time-varying exposures, age at vaccination for time-fixed exposures to reflect age-related eligibility.			
	We require continuous pharmacy and medical enrollment in HealthVerity prior to index date (FDA EUA date per vaccine) for follow-up. This is in order to establish pre-existing health status, which would have been queried at study entry in the clinical trials.			
	We require continuous California/Louisiana residency to maximize pre-index capture of vaccines, as people living outside of California /Louisiana would not have prior vaccines well captured in the registry.			
	Throughout, we will exclude people who are currently pregnant, using a validated			

- Exclusion criteria
 - Pregnant
 - Treatment with immunosuppressive therapy or diagnosis with an immunocompromising condition
 - History of COVID-19

gestational age algorithm with up to 9 months lookback. 18

Except in aim 4, where the analyses are specific to immunocompromised persons, we will exclude immunocompromised people considering claims for medications dispensed as well as and diagnosis codes.

We will exclude persons with a diagnosis of COVID-19 in any setting ≤ 90 days prior to index. We are limiting to 90 days as reinfections have become more common over the pandemic and were rare during the Fall 2020 clinical trial period. We believe 90 days represents a reasonable period in which persons then can be considered to be at risk for reinfection, and also are eligible for vaccination. ¹⁹

We will exclude individuals with discrepancies in sex and/or year of birth between HealthVerity claims and California/Louisiana immunization registry datasets, as these are key confounders in all analyses. Secondary deidentified data makes it impossible to reconcile differences, which would be expected to be resolved with primary data collection.

Treatment strategies

Receive 1 dose of a BNT162b2 adapted formulation vs. no BNT162b2 formulation or other COVID-19 vaccine (XBB.1.5 or BA.4/5 depending on timing)

All persons will be considered unvaccinated from date of US Food and Drug Administration (FDA) date of vaccine authorization/approval until, where applicable, 13 days after receipt of vaccine. In order to allow for time after dose for meaningful immunologic protection to accrue, persons will be considered vaccinated 14 days after vaccination. ^{20,21}

- For BA.4/5 vaccine in adults: FDA emergency use authorization date 31 August 2022⁴
- For XBB.1.5 vaccine: FDA approval date 11 September 2023²

Assignment procedures

Randomization: Eligible participants randomly assigned to receive dose of BNT162b2 XBB.1.5 vs. no BNT162b2 XBB.1.5

Adjustment for confounding factors which might influence a person's probability of exposure, using direct adjustment in time-varying exposure models and inverse probability of treatment weighting (with doubly robust adjustment, if necessary) in time-fixed exposure models.

Outcome(s)

Confirmed COVID-19

Medically attended COVID-19, as

- A COVID-19-related encounter, regardless of setting (primary outcome)
- An outpatient encounter with ICD-10-CM U07.1 "COVID-19" code
- An inpatient encounter with ICD-10-CM U07.1 "COVID-19" listed in any diagnosis position. As a sensitivity analysis, we will restrict to U07.1 in primary diagnosis field.
- An emergency department encounter with ICD-10-CM U07.1 "COVID-19" code
- Critical illness, defined as intensive care unit [ICU] admission, mechanical ventilation, or inpatient death. If sample size allows, we will evaluate VE against each component separately in order to support V&E models, including where possible ICU with and without mechanical ventilation.
- An urgent care visit with ICD-10-CM U07.1 "COVID-19" code

And separately, not necessarily due to COVID-

- All-cause mortality within 3-months of COVID-19 encounter, regardless of setting
- All-cause mortality within 3-months of COVID-19 outpatient encounter
- All-cause mortality within 3-months of COVID-19 inpatient encounter

All-cause mortality within 3-months of COVID-19 emergency department encounter
11. All-cause mortality within 3-months of COVID-19 critical illness

 All-cause mortality within 3-months of urgent care encounter for COVID-19

Note: aim 2 has additional non-COVID-19 respiratory illness outcomes and aim 5 has influenza outcomes. They are not represented here as the purpose of this chart is to demonstrate the target trial framework, and these outcomes were not assessed in clinical trials for licensure.

Follow-up

Analysis is limited to individuals still at risk on day 14 after vaccination/randomization

Unvaccinated follow-up time will occur from the date of FDA authorization/approval until 13 days after the receipt of vaccination, the outcome of interest, or are censored at the first of the following: 6 months of follow-up, end of medical and/or pharmacy enrollment, receipt of a non-Pfizer BioNTech vaccine or receipt of a second BNT162b2 COVID-19 vaccine dose.

Vaccinated follow-up time will occur from 14 days after the receipt of vaccination until the outcome of interest or are censored at the first of the following: 6 months of follow-up, end of medical and/or pharmacy enrollment, receipt of a non-Pfizer BioNTech vaccine or receipt of a second BNT162b2 COVID-19 vaccine dose.

Causal contrasts of interest

Per-protocol effect

Observational analog of the per-protocol effect, using sensitivity analyses and negative control outcomes to examine the quantitative impact of design and analytic assumptions.

Statistical analysis

In BNT162b2 Fall 2020 clinical trial, VE estimated as (1-IRR)*100, comparing vaccinated with unvaccinated persons, where IRR is the incidence rate ratio per 1000 person-years.

VE estimated as (1-aHR) for aims 1, 2 and 4 (time-varying exposures), and (1-aRR) for aim 5 (time-fixed exposure).

In mRNA-1273 Fall 2020 clinical trial, (1-
aHR)*100.

8.2. Setting

Patients who were California or Louisiana residents in the HealthVerity claims database will be defined using the following hierarchical definition:

- Persons who have their enrollment file record indicating a patient location of California or Louisiana in HealthVerity claims enrollment file.
- 2. Persons who have a patient state location other than California or Louisiana in HealthVerity claims enrollment but have one or more records in the California or Louisiana Immunization Registry. Examples include people who previously lived in Texas but moved to California and received a vaccine, or persons who crossed state lines for a vaccine and remain in their non-California state in claims data.

XBB vaccinations will be enumerated using the following hierarchical definition:

- Any person in HealthVerity claims data who has a record in the California/Louisiana Immunization Registry with a CVX code indicating having received the BNT162b2 XBB.1.5 monovalent mRNA vaccine will be considered vaccinated 14 days after registry event date.
- Any person in HealthVerity claims data who does not have a record in the California/Louisiana Immunization Registry but has a pharmacy claim with an NDC code indicating a BNT162b2 XBB.1.5 monovalent mRNA vaccine dose will be considered vaccinated 14 days after claim date.
- 3. Any person in HealthVerity claims data who does not have a record in the California/Louisiana Immunization Registry and does not have a pharmacy claim with an NDC code indicating a BNT162b2 XBB.1.5 monovalent mRNA vaccine dose but has a medical claim with a CPT code indicating a BNT162b2 XBB.1.5 monovalent mRNA vaccine dose will be considered vaccinated 14 days after claim date.
- 4. Any person in HealthVerity claims data who does not have a record in the California/Louisiana Immunization Registry, does not have a pharmacy claim with an NDC code indicating a BNT162b2 XBB.1.5 monovalent mRNA vaccine dose and does not have a medical claim with a CPT code indicating a BNT162b2 XBB.1.5 monovalent mRNA vaccine dose will be considered BNT162b2 XBB.1.5 unvaccinated.

BA.4/5 vaccinations will be enumerated in the same manner as XBB.1.5. For influenza, herpes zoster and pneumococcal vaccinations, Pfizer has not yet licensed these specific California/Louisiana state registries; instead, we will rely wholly on NDC and CPT codes in administrative claims.

Endpoints, patient characteristics, clinical characteristics, healthcare utilization, and any variables for the analysis will be derived from the HealthVerity claims database restricted to the state of California/Louisiana. Medical settings of outpatient, ambulatory, pharmacy, emergency department, and hospital will be included in the analysis for all variables. Urgent care visits will be considered separately from emergency department visits, as differences in the populations associated with urgent care as compared to emergency department encounters are expected.

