8.3. Variables

TABLE 3. EXPOSURE VARIABLES

Variable	Data source(s)	Operational definition
BNT162b2 XBB.1.5 mRNA vaccine after FDA authorization date and 14 or more days	California/Louisiana Immunization Registry as well as HV Claims	Vaccines will be enumerated as per section 8.2. Date of vaccination will be used to assess time-based inclusion/exclusion criteria.
BNT162b2 BA.4/5 mRNA vaccine after FDA authorization date and 14 or more days	California/Louisiana Immunization Registry as well as HV Claims	Vaccines will be enumerated as per section 8.2. Date of vaccination will be used to assess time-based inclusion/exclusion criteria.
Influenza vaccine	HV Claims	Identified using NDC or CPT code

TABLE 4. OUTCOME VARIABLES

Variable	Data source(s)	Operational definition
COVID-19 diagnosis	HV Claims	Any encounter regardless of diagnosis position or setting with ICD-10-CM code: U07.1
COVID-19 hospitalization	HV Claims	Inpatient encounter at an acute care facility with ICD-10-CM code: U07.1 "COVID-19" listed in any diagnosis position
COVID-19 emergency department visit	HV Claims	Emergency department visit with ICD-10-CM code: U07.1

Variable	Data source(s)	Operational definition
COVID-19 outpatient encounter	HV Claims	Outpatient encounter with ICD-10-CM code: U07.1
COVID-19 critical illness	HV Claims	Intensive care unit [ICU] admission, mechanical ventilation, or inpatient death
All-cause mortality	HV Mortality Database	HealthVerity ID in Mortality Database
Non-COVID-19 respiratory infections (pneumonia, RSV, rhinovirus, antibiotic prescriptions)	HV Claims	Any encounter regardless of setting with ICD-10- CM code for diagnosis or NDC codes for antibiotics (Codes in Annex)
Hospitalization length of stay (days)	HV Claims	Date of service end – date of service
ICU admission	HV Claims	As per HealthVerity's suggestion, ICU related services/inpatient stays will be found on Institutional claims, and can be identified using revenue codes (codes in Annex).
Invasive ventilation	HV Claims	CPT, HCPCS and ICD-10 (codes in Annex)
Cost of hospitalization	HV Claims	Using HealthVerity's "Proxy Financial Algorithm", based on CMS Medicare prospective payment system fee schedules
Influenza diagnosis	HV Claims	Any encounter regardless of setting with ICD-10- CM code: J09-J11
Influenza hospitalization	HV Claims	Inpatient encounter with ICD-10-CM code: J09- J11 listed as in any diagnosis position

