To quantify differences in VE of BNT162b2 formulations in non-pregnant, nonimmunocompromised adults when co-administered with seasonal influenza vaccines versus when each vaccine is given separately, by age groups.

> Main summary measure: aRR to evaluate non-inferiority, comparing people with coadministered vaccines to BNT162b2 vaccine alone for COVID-19-related outcomes

> Main summary measure: aRR to evaluate non-inferiority, comparing people with coadministered vaccines to seasonal influenza vaccine alone for influenza-related outcomes

Figure 4. Aim 5 study design

Exposure: Co-administration will be defined as same-day receipt of BNT162b2 vaccine and any formulation of seasonal influenza vaccine (for individuals 65+, only enhanced influenza vaccines).

Follow-up time: From 14 days after vaccination (index date). until the outcome of interest, or are censored at the first of the following: 6 months of follow-up, end of medical and/or pharmacy enrollment, receipt of any post-index COVID-19 or influenza date vaccine.

Outcomes of interest, for co-administered vaccines versus BNT1621b2 XBB.1.5 monovalent alone: Primary outcome:

- A COVID-19-related encounter, regardless of setting (primary outcome)
- Secondary outcomes:
 - An outpatient encounter with ICD-10-CM U07.1 "COVID-19" code

- An inpatient encounter with ICD-10-CM U07.1 "COVID-19" listed in any diagnosis position. As a sensitivity analysis, we will restrict to U07.1 in primary diagnosis field.
- An emergency department encounter with ICD-10-CM U07.1 "COVID-19" code
- All-cause mortality
- Negative control outcomes such as accidental injury, ingrown toenail or atopic dermatitis.

Exploratory outcome:

An urgent care encounter with ICD-10-CM U07.1 "COVID-19" code

Outcomes of interested, for co-administered vaccines versus seasonal influenza vaccine alone:

Primary outcome:

A flu-related encounter, regardless of setting (primary outcome)

Secondary outcomes:

- An outpatient encounter with ICD-10-CM code indicating influenza
- An inpatient encounter with influenza. Note, influenza will not be required to be the principal
 diagnosis as there is less concern about incidental findings and previous experience from the
 flu team suggests primary diagnosis coding in influenza hospitalizations might prioritize
 complications rather than the infection.
- 3. An emergency department encounter with ICD-10-CM code indicating influenza
- 4. All-cause mortality

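### Aim 5 finds XBB.1.5 doses through the registry but influenza doses only through claims, so some co-administered people will be counted as BNT162b2 alone; the plan neither lists nor examines the resulting bias.

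*Protocol*

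**What the plan says.** Protocol 8.2 (Setting) looks for XBB.1.5 doses in the registry first. A person counts as vaccinated if he or she "has a record in the California/Louisiana Immunization Registry with a CVX code indicating having received the BNT162b2 XBB.1.5 monovalent mRNA vaccine". Pharmacy NDC claims, and then medical CPT claims, are the fallback for people with no registry record. The state registries for influenza vaccine are not licensed, and for those doses the protocol says "we will rely wholly on NDC and CPT codes in administrative claims". Table 3 in 8.3 agrees: the source for influenza vaccine is HV Claims, "Identified using NDC or CPT code".

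Section 6 gives the reason for linking the registries. Roster billing produces no individual claim, so in traditional claims databases "vaccinations conducted via roster billing were lost".

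For Aim 5 (8.7.6), "Co-administration will be defined as same-day receipt of BNT162b2 vaccine and any formulation of seasonal influenza vaccine". The main summary measure for the affected contrast is an "aRR to evaluate non-inferiority, comparing people with coadministered vaccines to BNT162b2 vaccine alone for COVID-19-related outcomes". No margin is given, and section 7 says the study "does not include any pre-specified hypotheses".

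Section 8.4.1 compares registry capture of COVID-19 doses with the California dashboard (72.2% against 72.9% for two wild-type doses). No similar check is described for influenza doses. The limitations in 8.9 do not mention the unequal sources. The one Aim 5 sensitivity analysis named is a 7-day instead of a 14-day exposure definition.

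**The concern.** Arm membership depends on two vaccinations that are ascertained with different completeness. The registry linkage repairs the gap in claims for the XBB.1.5 half of the exposure and leaves it open for the influenza half. A person given both vaccines at a roster-billed site has a registry XBB.1.5 record and no influenza claim, and the rules class that person as BNT162b2 alone. This error puts recipients of the test exposure into the comparator.

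That matters because the contrast is meant to evaluate non-inferiority. Mixing co-administered people into the comparator tends to hide a real loss of protection, provided those people are otherwise like the ones who were captured. A large sample does not help, because it tightens the interval around a biased value. Weighting does not reclassify anyone. Negative control outcomes would not reveal the error when missed and captured people have equal risk.

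Other Aim 5 rules rest on the same influenza claims: the exclusion for influenza vaccination between 1 August and 10 September 2023, the exclusion by influenza vaccine type at age 65 and over, and censoring at a later influenza vaccine.

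**Working it through.** **Inputs.** From the documents: the dose sources (8.2, Table 3), the loss of roster-billed doses (section 6, not quantified), the same-day definition (8.7.6) and the expected adult XBB.1.5 doses in California (8.5). Assumed, because the documents give none of them: p, the true share of XBB.1.5 recipients who were co-administered; m, the share of those whose influenza dose left no claim; the true RR; and a non-inferiority margin.

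**1. The plan's own figure.** 0.75 × 12,000,000 × 0.16 × 0.60 = 864,000, as stated in 8.5. It is not an Aim 5 sample size; it comes before the Aim 5 exclusions and leaves out Louisiana. It is used here only for scale.

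**2. Contamination of the BNT162b2-alone arm.** c = pm / (1 − p + pm). With p = 0.5 and m = 0.3, c = 0.15 / 0.65 = 0.231.

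**3. Observed RR if missed and captured people have equal risk.** RR_obs = RR / [1 + c(RR − 1)]. With RR = 1.25 and c = 0.231, RR_obs = 1.25 / 1.058 = 1.18. Over a range, each cell gives c and then the observed value of a true RR of 1.25:

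| p | m = 0.1 | m = 0.3 | m = 0.5 |
|---|---|---|---|
| 0.3 | 4%, 1.24 | 11%, 1.22 | 18%, 1.20 |
| 0.5 | 9%, 1.22 | 23%, 1.18 | 33%, 1.15 |
| 0.7 | 19%, 1.19 | 41%, 1.13 | 54%, 1.10 |

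With m = 0, c = 0 and there is no distortion. A true RR of 1.00 stays at 1.00 throughout.

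**4. Effect on a non-inferiority conclusion, same condition.** Take 864,000 recipients, p = 0.5, m = 0.3, one-sided 0.025 and a true RR equal to the margin. A normal approximation on log RR is used, with risks in the truly-alone group of 0.1% and 1% (100 and 1,000 per 100,000, borrowed from the incidence grid in section 5.5 of the Aim 1 SAP). The observed arms are 864,000 × 0.5 × 0.7 = 302,400 co-administered and 561,600 alone.

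- Margin 1.25, risk 0.1%: arm risks 0.00125 and 0.001058, SE = 0.066. The distance from observed RR to margin is log(1.25/1.182) = 0.056. The chance of declaring non-inferiority is Φ(0.056/0.066 − 1.96) = 0.13.
- Margin 1.25, risk 1%: SE = 0.021, chance 0.77.
- Margin 1.10: 0.05 and 0.18 at the two risks.

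With complete influenza capture each of these is 0.025.

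**5. Unequal risk.** Let missed co-administered people have k times the risk of captured ones. The captured group's risk relative to truly-alone people is r = RR / (1 − m + mk), and RR_obs = r / [(1 − c) + ckr]. With p = 0.5 and m = 0.3:

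- k = 0.8, RR = 1.00: r = 1/0.94 = 1.064, and RR_obs = 1.064 / (0.769 + 0.196) = 1.10. A true RR of 1.25 is observed as 1.31.
- k = 1.25: a true RR of 1.00 is observed as 0.90, and 1.25 as 1.05.

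Modest differences in risk can therefore reverse or enlarge the distortion.

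**6. The other contrast.** A missed influenza dose moves a co-administered person into the BNT162b2-alone arm. It does not place anyone in the influenza-alone arm.

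**The case against.** The strongest objection concerns direction. A reader might infer that the error must pull the aRR toward 1 and so must favour non-inferiority. The documents do not support that as a certainty. COVID-19 outcomes come from the same claims as influenza doses, so people with little billed care may have both fewer captured influenza doses and fewer recorded COVID-19 encounters. That is the k < 1 case in step 5, which moves the aRR the other way. This part of the objection stands, and the attenuation has to be stated with its condition.

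Size is also open. Section 6 does not quantify roster billing, and 8.4.3 argues that claims should include almost every billed encounter. That passage concerns encounters and does not answer section 6, but m may be small: at p = 0.5 and m = 0.1, 1.25 becomes only 1.22. The registry is not complete either, since 8.4.1 exempts Defense, Veterans Affairs and Indian Health sites.

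There is a partial mitigation. Table 5 adds the registry's administration setting as an Aim 5 covariate for the propensity score, and setting bears on where roster billing occurs. It balances the arms as classified but leaves the misclassified people where they are.

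Finally, Aim 5 is exploratory, its list of sensitivity analyses is left open, and the SAPs supplied cover Aims 1, 2 and 3B only. An Aim 5 SAP may deal with this. The protocol discloses the source choice but not its consequence for the arms.

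**Conclusion.** The mechanism holds on the protocol's own terms. The BNT162b2-alone arm will contain some co-administered people, and nothing in the plan supplied detects, bounds or discloses this. If missed and captured co-administered people have equal outcome risk after weighting, the aRR for this contrast is attenuated toward 1. Over assumed p of 0.3 to 0.7 and m of 0.1 to 0.5, a true RR of 1.25 is observed as 1.24 to 1.10. If the risks differ, the bias can go either way.

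The values of p, m, the true RR and the margin are all assumptions, so these figures show what could happen and do not estimate the actual bias. The point is limited to the contrast with BNT162b2 alone in an exploratory aim. It should be dealt with before any non-inferiority statement is made.

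**What to change.** In the Aim 5 SAP, or by protocol amendment:

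- Alongside the registry-inclusive analysis, pre-specify an analysis of co-administered versus BNT162b2 alone that is restricted, in both arms, to people whose index XBB.1.5 dose also has a pharmacy (NDC) or medical (CPT) claim on or within a few days of the registry date. State the window.
- Report the share of registry XBB.1.5 doses with no matching claim, overall and by administration setting, as an internal guide to claims capture.
- Add a quantitative bias analysis over a range of influenza capture, using the formulas above and letting risk differ between missed and captured people.
- Make any non-inferiority statement conditional on agreement between these analyses.
- List the limitation in 8.9.

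The work uses data already held: a filter, a cross-tabulation, a short calculation and some wording. The restricted analysis has fewer recipients, applies only to claims-billed doses, and assumes without test that two doses given at one visit are billed alike. It also selects people on billing. For these reasons it is proposed as a companion and not as a replacement for the main analysis.
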